**The following demographic and clinical information will be collected for both Phase 1 and Phase 2 of this study:**

#### **Cardinal Demographic and Clinical Features**

- Gender
- Age
- Race/Ethnicity
- Occupations
- Date of first asbestos exposure
- Highest education completed. One year of apprenticeship equals one year of college
- Height
- Weight
- Co-morbidities
- Social Hx (smoking, drinking, recreational drug use)
- Current list of medications, including OTC and “natural” remedies

### **Case-Matched Controls**

- Age
- Gender
- Ethnicity
- Co-morbidities
- Presence of benign responses to asbestos exposure (Plaques, pleural thickening, etc.)
- Smoking status

### **Disease type and severity stratification**

- Presence of mesothelioma
- Disease stage classification (IMIG)
- Date of initial mesothelioma diagnosis
- Histologic data
- Radiographic data
- Nature of exposure Acute/chronic exposure
- Presence of benign disease indicators (asbestosis, pleural plaques, thickening of the pleura)

### **Potential Test confounders**

- When did you last smoke
- When did you last drink and what was it
- When did you last eat and what was it
- Time since brushing teeth, or rinsing with anything other than distilled water
- Nebulized inhaled medication less than 2 hours prior to breath collection

**G. Data Analysis:** Phase 1, which is designed to identify putative VOC markers, will be non-randomized and non-blinded. Statistical analysis will be performed by both the Owlstone and Fujirebio laboratories using their trained biostatisticians. Selected biomarkers will then be used in Phase 2. Study subjects in Phase 2 will be anonymized and the Owlstone and Fujirebio laboratory staff will be blinded with regards to disease presence.

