### **H. Materials and Methods:**

(1) Breath sampling masks, collection tubes and the collection apparatus will be provided by Owlstone Medical Ltd (OML) (\$300/breath sampling kit for 300 subjects). OML has developed a breath sampling system for the collection of human breath samples that is comprised of two main parts:

1. ReCIVA® Breath Sampler: the breath sample collection unit, and
2. CASPER: the air supply unit.

The intended use of ReCIVA is to collect samples of Volatile Organic Compounds (VOCs) present in exhaled breath for subsequent laboratory analysis. CASPER is used to provide a filtered ambient air supply to the ReCIVA breath sampler.

The Insulators Union considers that use of the OML breath sampling system as part of the study constitutes use of a diagnostic test system in the laboratory research phase of development. The Insulators Union also considers that the OML breath sampling test system meets the requirements for exemption of diagnostic devices from part 812 IDE regulations as set out in part 812.2(c)(3). The OML devices will therefore be deployed as "Research Use Only" (RUO) products for the purposes of the study. A detailed description of the OML breath sampling system, including a risk assessment, can be found in reference OW-019034-RE attached as part of this IRB submission package.

(2) The serum-based assays will be provided free of charge by Fujirebio.

(3) Statistical Analysis: Descriptive statistics from the study population and statistics intended to determine the predictive capability, sensitivity and specificity of the Owlstone Breath Biopsy, will be conducted by Owlstone biostatisticians. Predictive capability, sensitivity and specificity of the Fujirebio Lumipulse Mesomark assay will be conducted by the Fujirebio biostatisticians.

[figure not shown]

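### Current work and recent workplace chemical contact are not recorded at breath sampling, so a case-control difference in work-related VOCs could not be detected or adjusted for

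*Combined protocol and SAP*

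**What the plan says.** Under "Potential Test confounders" in section F, five items are recorded. The first is "When did you last smoke". Two more ask for the timing and content of the latest drink and the latest meal. A fourth asks how long ago the participant cleaned the teeth or used a mouth rinse, and the fifth covers use of a nebulizer shortly before sampling.

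The exclusion criteria add a 2-hour restriction on food, smoking, nebulized medication and alcohol. The demographic list includes occupations and the date of first asbestos exposure, and the disease stratification list includes whether exposure was acute or chronic. None of these gives current work status or the timing of contact with other chemicals.

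The matching factors under Case-Matched Controls are age, gender, ethnicity, co-morbidities, benign asbestos-related findings and "Smoking status". Occupation and work status are not among them. On the air breathed during collection, section H(1) says that "CASPER is used to provide a filtered ambient air supply to the ReCIVA breath sampler". Sections G and H(3) describe no covariate adjustment. The same eligibility criteria apply to both aims.

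**The concern.** The outcome is the breath VOC profile itself, and the confounder list accepts that recent outside sources of VOCs can distort it. Solvents, adhesives, paints and fuels met at work belong to the same class but are missing from the list. Participants must report past asbestos exposure, so many will have a trade background.

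The two groups could plausibly differ in current work. Section B(1) gives mesothelioma a median survival of 9 months untreated and 12 months with intervention, whereas controls have benign pleural change. Age matching does not by itself equalise work status between them. A work-related VOC that is more common in controls would look like a VOC lowered by mesothelioma.

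Nothing in the plan would reveal this. Filtered air acts while the sample is taken, and the documents do not say that it deals with VOCs absorbed earlier. Blinding in Phase 2 guards against biased reading, not against a real exposure difference. Phase 2 uses the same criteria and could carry the same imbalance. Recent exposure not asked about at sampling cannot be reliably reconstructed later.

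**Working it through.** The plan gives no figure to reproduce here: no alpha, power, effect size or exposure share is stated. The calculation is an illustration of scale.

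**Inputs from the documents.** Phase 1 has 100 controls and 100 cases; Phase 2 has 65 controls and 35 cases (section F).

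**Assumed inputs.** Share recently exposed: p0 in controls (10% to 40%) and p1 in cases (5%). Exposure raises the VOC by s = 1 or 2 SD. The test is two-sided at 0.05 for one VOC.

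**Formulas.**

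- Mean difference: d = s × (p0 − p1)
- Variance in each group: v = 1 + s² × p × (1 − p)
- Test statistic: z = d / √(v0/n0 + v1/n1)
- Chance of p<0.05: Φ(z − 1.96) + Φ(−z − 1.96)
- AUC: the chance that a random control has a higher value than a random case, i.e. 0.5 + (p0 − p1) × (Φ(s/√2) − 0.5)

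**Worked case, 30% v 5%, s = 2.**

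- d = 2 × 0.25 = 0.50
- v0 = 1 + 4 × 0.30 × 0.70 = 1.84; v1 = 1 + 4 × 0.05 × 0.95 = 1.19
- Standardised difference = 0.50 / √((1.84 + 1.19)/2) = 0.41
- Phase 1: z = 0.50 / √(1.84/100 + 1.19/100) = 2.87, chance 82%
- Phase 2: z = 0.50 / √(1.84/65 + 1.19/35) = 2.00, chance 52%
- AUC = 0.5 + 0.25 × (Φ(1.414) − 0.5) = 0.61

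| Controls v cases exposed | Rise | Phase 1 | Phase 2 | AUC |
|---|---|---|---|---|
| 40% v 5% | 2 SD | 98% | 79% | 0.65 |
| 30% v 5% | 2 SD | 82% | 52% | 0.61 |
| 15% v 5% | 2 SD | 23% | 13% | 0.54 |
| 10% v 5% | 2 SD | 10% | 7% | 0.52 |
| 20% v 5% | 1 SD | 17% | 11% | 0.54 |
| 10% v 5% | 1 SD | 6% | 6% | 0.51 |

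With equal shares in the two groups, d = 0 and there is no bias.

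**Multiplicity.** Phase 1 will screen many compounds. The documents give neither their number nor a correction. For an assumed 100 compounds tested at 0.05/100, the Phase 1 chance falls from 98% to 68% at 40% v 5%, from 82% to 27% at 30% v 5% (both 2 SD), and from 17% to about 1% at 20% v 5% (1 SD).

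**Ceiling on one marker.** However large the rise, the AUC cannot exceed 0.5 + (p0 − p1)/2. At 40% v 5% that is 0.5 + 0.35/2 = 0.675. Significance is less bounded: if the VOC is simply present or absent at 20% v 5%, a comparison of proportions gives 90% in Phase 1 and 53% in Phase 2, with an AUC of 0.575.

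**The case against.** The strongest reply is that the causal premise is not in the documents. No section says that controls are at work, are union members or handle solvents. The union appears in section H(1) only as taking a position on the device's regulatory status. Past asbestos exposure is required of both groups. Section B(1) gives a latency of 40 to 50 years and a median age at diagnosis of 65, and controls are matched on age and co-morbidities, so many in both groups may be retired. This stands: the difference in work is an inference, and the bias is conditional on it.

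A reader might also infer that a work-related VOC would be selected and then validated as a disease marker. The documents do not support that. Section F judges Phase 2 by sensitivity, specificity and predictive values, not by p<0.05, and allows the study to stop if predictive capability is too low. That rule has no threshold, but a single marker with an AUC of 0.51 to 0.65 is a poor candidate to pass. Several work-related VOCs occurring together could still enter a panel, which these figures do not cover.

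Third, it would be wrong to say that occupation is unrecorded. A crude proxy exists, and only recency is missing. Sections C and D also refer to an IRB application and a breath-sampling guide that are not available here, so a fuller questionnaire cannot be ruled out.

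None of this answers the omission itself. If the groups turn out alike in recent exposure, the present forms cannot show it.

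**Conclusion.** The concern holds in a limited, conditional form. Recent smoking, drink, food, oral rinsing and nebulized medication are recorded, and occupations are listed, but current work status and recent workplace or solvent contact are not recorded, restricted or matched. If cases and controls differ in current work, VOCs absorbed before sampling could contribute to the Phase 1 difference and recur in Phase 2.

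The size is unknown and ranges from negligible to substantial with the assumed exposure gap. Even at the top of that range, one such VOC discriminates weakly. The documents do not show that the bias is present, or that it would carry a false marker through validation. This is a cheap improvement, justified because the information is lost unless it is taken at sampling.

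**What to change.** In both phases, add two items to the confounder list in section F:

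1. Date and time of the last work shift, or that the participant is not working.
2. Any recent contact with solvents, adhesives, paints or fuels, with the look-back window set by the breath laboratory. The documents give no basis for a particular window.

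Add to the analysis text:

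- Report both items by group in each phase.
- In Phase 1, report each candidate VOC's case-control estimate with and without adjustment for recent exposure, and flag those whose estimate is materially reduced.
- In Phase 2, repeat the accuracy estimates among participants without recent exposure, as a sensitivity analysis.

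Two further steps are tempting but not advised. Matching on work status is debatable because stopping work may be a consequence of the disease, and at 30% v 5% it would restrict the usable controls appreciably. Dropping VOCs that lose significance in an unexposed subset could discard true markers merely because the subset is smaller. Reporting both estimates avoids each problem.

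The cost is two form items and a less precise subset estimate. At 30% v 5%, the Phase 2 subset would hold about 65 × 0.70 = 45.5 controls and 35 × 0.95 = 33 cases. The interval for specificity would widen by a factor of about √(65/45.5) = 1.20, and that for sensitivity would hardly change. With so few exposed cases (about 5 of 100 in Phase 1), the adjusted estimates would take their information on exposure mainly from controls and should be read as a check, not as the primary result.

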**(2) Project Rationale:** This study seeks to identify markers for mesothelioma using a non-invasive technique which samples volatile organic compounds (VOC) in the breath of test subjects (Owlstone Medical Ltd, Cambridge, England). A comparison will be made with an FDA-approved, serum-based assay (Lumipulse Mesomark, Fujirebio Diagnostics Inc., Malvern, PA). Identifying patients who are either predisposed to developing mesothelioma by pleural findings as an indication of asbestos exposure or who may be at an early disease stage, is expected to improve prognosis by limiting disease progression through more effective medical and surgical therapeutics.

**(3) Purpose of Study and/or Hypothesis:** Individuals with pleural mesothelioma are anticipated to have a different volatile organic compound (VOC) profile in comparison with appropriately matched controls. These specific compounds may have a diagnostic potential which enables the early detection of patients with disease before overt clinical symptoms become manifest. Following the identification of putative

biomarkers, the predictive capability of these markers alone and in concert with a serum-based assay, will be tested.

**(4) Anticipated Outcome:** We anticipate that one or more VOC markers in breath samples from affected subjects will be identified using the Owlstone Breath Biopsy sampling methodology which will show an association with the presence of pleural mesothelioma in patients. Furthermore, we will evaluate participant's Lumipulse Mesomark serum assay, comparing those results with the VOC profile to discern parameters of efficacy.

**(5) Importance/Relevance:** Identifying patients who are either likely to develop mesothelioma or who are at an early disease stage, is expected to improve prognosis by limiting disease progression through more effective medical and surgical therapeutics.

**C. References and Supporting Data:** See accompanying Owlstone's Breath Biopsy® The Complete Guide Second Edition as part of this IRB submission and the two 2004 American Radiology Letters to the Editor consisting of a response to a peer-reviewed article on chest radiograph B-readers and the author's reply.

**D. Detailed Plan of Proposed Research:** As submitted in the IRB A-1 Research Application document.

**E. Specific Objectives or Aims:** Specific Aim 1: Identify putative VOC biomarkers in the breath samples of subjects with mesothelioma in comparison with case-matched controls.

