Specific Aim 2: Test the predictive capability of VOC biomarkers and serum-based mesothelioma biomarkers both individually and collectively.

**F. Experimental Design:** This will be a prospective, non-randomized, case-controlled study. In Specific Aim 1, the disease status of the study population will not be blinded to the investigators in order to select disease-specific biomarkers. In Specific Aim 2, the Investigators and the analytics team will be blinded to the presence of disease to determine the predictive value of the markers. Predictive capability will be defined by determining the sensitivity, specificity and positive and negative predictive capability of the selected VOC biomarkers in identifying subjects with mesothelioma. In addition, study subjects will also be tested with an FDA approved, serum-based ELISA assay (Lumipulse, Mesomark, Fujirebio). The predictive capabilities of both tests will be evaluated both individually and collectively.

Phase 1 - Discovery of VOCs associated with the presence of mesothelioma: A total of 200 volunteers - 100 with objective evidence of exposure to asbestos and no evidence of mesothelioma, and 100 with histologically confirmed evidence of mesothelioma - will be recruited into this phase of the study with an expected study duration of up to 24 months. Objective evidence of asbestos exposure for purposes of this study include, but may not be limited to, a history of exposure to asbestos and bilateral pleural plaques or bilateral pleural thickening. Radiographic evidence of exposure will be rendered by an A reading, B reading, or an interpretation of a radiologist board certified by the American College of Radiology.

Phase 2 - Validation study to assess the predictive capability, sensitivity and specificity of selected VOCs in identifying subjects with mesothelioma: A total of 100 volunteers - 65 with objective evidence of

asbestos exposure and no evidence of mesothelioma, and 35 with objective evidence of mesothelioma - will be recruited into this phase of the study with an expected duration of up to 12 months. The investigators and testing laboratories will be blinded as to the presence of mesothelioma among the participants.

Phase 2 is contingent on the successful identification of VOCs during the Phase 1 discovery study. If no putative biomarkers are identified in Phase 1 of this study or if the predictive capability proves to be too low, the study will be discontinued.

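### Section G leaves Phase 1 non-blinded without limit, so nothing keeps disease status from breath-laboratory staff who process and exclude VOC data before markers are selected

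*Combined protocol and SAP*

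**What the plan says.** Section G (Data Analysis) describes the discovery phase in one sentence: "Phase 1, which is designed to identify putative VOC markers, will be non-randomized and non-blinded". It exempts no role. It continues: "Statistical analysis will be performed by both the Owlstone and Fujirebio laboratories using their trained biostatisticians". Section H assigns the statistics for the breath test to the breath laboratory's biostatisticians in particular.

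Laboratory blinding appears only for the second phase. Section G: "Study subjects in Phase 2 will be anonymized and the Owlstone and Fujirebio laboratory staff will be blinded with regards to disease presence". Section F (Experimental Design) says of Phase 2: "The investigators and testing laboratories will be blinded as to the presence of mesothelioma among the participants". For Aim 2 it says that "the Investigators and the analytics team will be blinded to the presence of disease".

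For Aim 1, Section F is narrower than Section G. It says that "the disease status of the study population will not be blinded to the investigators in order to select disease-specific biomarkers". That is the only reason given for open status, and laboratory staff are not mentioned.

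Section F also makes Phase 2 depend on Phase 1: it stops the programme if no marker is found, and adds that "if the predictive capability proves to be too low, the study will be discontinued". For the detailed plan, Section D says only: "As submitted in the IRB A-1 Research Application document".

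**The concern.** A VOC table is not a raw reading. People decide how peaks are processed, which runs fail quality control and which samples are excluded. If those people know which samples come from mesothelioma patients, their decisions can line up with disease status. An artefact may then look like a marker, or a true marker may be lost.

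The reason given for open status does not reach these steps. Selecting disease-specific markers means comparing cases with controls, which needs disease status only once the measurements are final.

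The stake is the discovery step. Phase 1 decides whether the study continues and which VOCs go forward. An artefact carried forward would use up the Phase 2 cohort of 100 (35 with mesothelioma). Phase 2 tests only the selected markers, so it cannot recover one missed in Phase 1.

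**Working it through.** **1. The blinding statements side by side**

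| Role | Phase 1 / Aim 1 | Phase 2 / Aim 2 |
|---|---|---|
| Investigators | Not blinded, for marker selection (F) | Blinded (F) |
| Analytics team | Not named; phase as a whole non-blinded (G) | Blinded (F) |
| Testing-laboratory staff | Not named; phase as a whole non-blinded (G) | Blinded (F and G) |
| Coding of subjects | None stated | Anonymized (G) |
| Lock of the VOC table before status is released | None stated | None stated |

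The biostatisticians who analyse Phase 1 belong to the testing laboratories (G, H). They cannot relate VOCs to disease without disease status, so the breath laboratory's organisation must hold it at some point in Phase 1. The supplied text does not say when it arrives or who inside the laboratory may see it.

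**2. Scope**

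Phase 1 has 100 + 100 = 200 subjects and Phase 2 has 65 + 35 = 100. The share in the phase with no stated laboratory blinding is 200/300 = 67%. This counts subjects; it does not measure bias.

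**3. Illustration of one mechanism, case-aware exclusion**

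The documents give no alpha, effect size, exclusion rate or number of VOCs, so there is no figure of the plan's own to reproduce. From the documents: 100 cases and 100 controls. Assumed: one VOC unrelated to disease, distributed N(0,1) in both groups; k = 5, 10 or 20 borderline samples per group (5%, 10%, 20%); a pooled two-sided t-test at 0.05.

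- Status known: drop every borderline case below the median and every borderline control above it. The mean number dropped in total is 2k × 0.5 = k.
- Status blinded: drop each borderline sample with probability 0.5, so the same mean number.

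Simulation, 100,000 runs per cell, Monte Carlo standard error at most 0.13 percentage points:

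| Borderline | Mean dropped | p<0.05, status known | p<0.05, blinded |
|---|---|---|---|
| 5% | 5 | 5.7% | 5.0% |
| 10% | 10 | 8.8% | 5.0% |
| 20% | 20 | 21.7% | 5.0% |

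Repeat runs gave 5.8%, 8.6% to 8.8% and 21.5% to 22.1% with status known, and 5.0% to 5.1% blinded.

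**4. Hand check of the simulation**

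A dropped value lies on average √(2/π) = 0.798 SD from the median. With k/2 dropped per group, n = 100 − k/2 remain, and each group mean moves 0.798 × (k/2)/n, in opposite directions. The difference is d = 2 × 0.798 × (k/2)/n and its standard error is √(2/n). The rejection rate is P(Z > 1.96 − d/SE) + P(Z < −1.96 − d/SE).

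- k = 5: n = 97.5, d = 0.041, SE = 0.143, d/SE = 0.286; rate 4.7% + 1.2% = 5.9%.
- k = 10: n = 95, d = 0.084, SE = 0.145, d/SE = 0.579; rate 8.4% + 0.6% = 8.9% before rounding the parts.
- k = 20: n = 90, d = 0.177, SE = 0.149, d/SE = 1.189; rate 22.1% + 0.1% = 22.1% before rounding the parts.

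The approximation agrees with the simulation.

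**The case against.** The strongest reply is that this is silence, not a stated flaw. Section F names only the investigators as unblinded and ties that to marker selection; Section G's sentence can be read as shorthand for it. This stands in part. A reader might infer that bench staff will be told who is a case, and the documents do not say so. What remains is that Section G sets no limit, status must reach the laboratory, and no barrier is described.

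Second, open discovery followed by blinded validation in 100 new volunteers is a recognisable design. A reader might conclude that the final sensitivity and specificity are compromised. That does not follow: the Phase 2 blinding protects those estimates and should expose many false markers. It does not protect marker selection or the decision to continue.

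Third, the illustration is extreme and partial. It needs staff to drop every unfavourable borderline result for one VOC, and at 5% borderline it adds less than one percentage point. With an assumed Bonferroni correction over 300 VOCs, the rates are 0.03%, 0.06% and 0.46% per VOC, against a nominal 0.05/300 = 0.02%. It models false markers only, not missed markers or wrongful stopping. All of this stands. A reader might instead assume a fixed shift between cases and controls, which gives 29.3% at 0.2 SD and 94.2% at 0.5 SD. That describes samples fully confounded with batch, not knowledge of status, and the documents do not support it.

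Fourth, the application document named in Section D, or the attachments, may already cover handling. That is possible. A short limit or cross-reference would then still be useful, because Section G as it stands reads as unrestricted.

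**Conclusion.** The point holds as a gap in a stated design rule, and a cheap improvement is available. Phase 1 is declared non-blinded without limit, the laboratories are blinded only in Phase 2, and the one reason given for open status does not require it during measurement.

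The size of any bias cannot be calculated from the documents. The range of about 6% to 22% per null VOC, against 5%, is a worst case resting on the assumed borderline share, test and exclusion rule. It is not an estimate for this study. The conclusion also assumes that the documents not supplied contain no Phase 1 blinding procedure. The harm is confined to a misdirected or wrongly stopped discovery step.

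The claim concerns the breath laboratory only. No harm is argued for the serum assay, and batch order and storage time are separate questions.

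**What to change.** Amend Section G to say that:

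1. Phase 1 breath samples go to the breath laboratory under study codes, without disease status.
2. Staff doing the assay, peak processing and quality control, including exclusions, stay blinded until the VOC table is locked.
3. Disease status is then released to the biostatisticians for marker selection. They take no part in processing or quality control, and any later change to the table is logged with its reason.

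If a document not supplied already provides for this, a cross-reference in Section G is enough.

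Sample size, eligibility and patient procedures do not change. The sponsor already accepts anonymized subjects and blinded laboratory staff for Phase 2, but describes no coding scheme or code holder. Existing study staff would have to set up the code before Phase 1 and hold it for up to 24 months. Marker selection must wait for the lock. The breath laboratory must keep its biostatisticians apart from processing and quality control, and the documents do not show whether that separation already exists.

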The following inclusion and exclusion criteria will apply to both Specific Aim 1 and 2 of this study.

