#### **Inclusion Criteria**

- Male or Female subjects over the age of 18
- Reported prior exposure to asbestos
- Radiologically confirmed bilateral pleural plaques or bilateral pleural thickening, or histologically confirmed mesothelioma

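### Do the Phase 2 blinding text and the split of analyses between the two laboratories prevent Aim 2 from being carried out?

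*Combined protocol and SAP*

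**What the plan says.** Three sentences describe the Phase 2 blind, and they name different parties.

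- Section F, on Aim 2: "the Investigators and the analytics team will be blinded to the presence of disease to determine the predictive value of the markers".
- Section F, Phase 2 paragraph: "The investigators and testing laboratories will be blinded as to the presence of mesothelioma among the participants".
- Section G: "the Owlstone and Fujirebio laboratory staff will be blinded with regards to disease presence". The investigators are not mentioned here. The same sentence says that Phase 2 subjects are anonymised.

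Disease status also enters at recruitment. Phase 2 takes 65 exposed controls, "and 35 with objective evidence of mesothelioma - will be recruited into this phase of the study". Section F states "The following inclusion and exclusion criteria will apply to both Specific Aim 1 and 2 of this study", and the criterion that separates the groups is "Radiologically confirmed bilateral pleural plaques or bilateral pleural thickening, or histologically confirmed mesothelioma". The data lists open with "The following demographic and clinical information will be collected for both Phase 1 and Phase 2 of this study", and the later list on disease type and severity includes "Presence of mesothelioma".

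On the analyses, Aim 2 (section E) and the design text (section F) both promise accuracy for the breath and serum tests separately and together. Section H(3) assigns descriptive statistics and breath-test accuracy to Owlstone's biostatisticians, and serum-test accuracy to Fujirebio's. No section names an owner or gives a rule for the combined result. Section D refers the detailed plan to the IRB A-1 application.

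**The concern.** There are two worries. First, eligibility and the 35/65 split are settled at enrolment, before any sample is analysed. If the investigators enrol and are also blinded to disease, unblinding later does not help, and the blind could not truthfully be reported as kept.

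Second, the accuracy of a combined test depends on how the two results fall together within each person. If each laboratory reports only its own sensitivity and specificity, that information is lost. Phase 2 is the study's only validation stage, so it could then not say whether breath sampling adds anything to the serum assay.

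A further worry follows from the unassigned roles. If disease status reached the laboratories' statisticians while a breath cut-off was still open, the reported accuracy would be too favourable.

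**Working it through.** **Counts.** Phase 2: 65 + 35 = 100, as stated. Both phases: 200 + 100 = 300, which matches the 300 breath kits in section H(1). The plan states no target accuracy, precision or power, so there is no sample-size figure to reproduce.

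**Blinding against recruitment.** A contradiction needs one person who must both know and not know disease status. Section F describes recruitment in the passive voice and names no recruiter. The investigators and analytics team in the Aim 2 sentence, the testing laboratories in the Phase 2 paragraph and the laboratory staff in section G can all stay blind if separate staff screen and enrol. Anonymised subjects whose sensitivity and specificity are computed later imply that someone holds the link to diagnosis. The texts can therefore all be satisfied together. What is missing is a name for the role.

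**Combined accuracy from single-test tables.** Let a and b be the numbers of correct results on the two tests among n people. Without the joint table, the number correct on at least one test lies between max(a, b) and min(n, a + b). The number correct on both lies between max(0, a + b − n) and min(a, b). The plan gives no accuracies, so the counts below are assumed: breath 25/35 cases and 52/65 controls correct, serum 21/35 and 58/65.

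| Rule | Sensitivity | Specificity | Youden index |
|---|---|---|---|
| Breath alone | 25/35 = 0.71 | 52/65 = 0.80 | 0.51 |
| Serum alone | 21/35 = 0.60 | 58/65 = 0.89 | 0.49 |
| Either positive | 25/35 to 35/35 = 0.71 to 1.00 | 45/65 to 52/65 = 0.69 to 0.80 | 0.41 to 0.80 |
| Both positive | 11/35 to 21/35 = 0.31 to 0.60 | 58/65 to 65/65 = 0.89 to 1.00 | 0.21 to 0.60 |

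For example, 52 + 58 − 65 = 45 controls at least are negative on both tests. A weaker assumed pair (breath 21/35 and 45/65, serum 18/35 and 58/65) gives an either-positive Youden index of 0.18 to 0.69, against 0.41 for the better single test. A stronger pair (30/35 and 58/65, 25/35 and 60/65) gives 0.67 to 0.89 against 0.75. Each either-positive range contains values above and below the better single test, so even the sign of the gain is open without the joint table. With a joint table of the same 100 subjects, each range becomes a single value.

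**Tuning the cut-off on Phase 2 data, as a conditional illustration only.** I simulated 20,000 validation samples of 35 and 65 with normal, unit-variance scores at each true area under the curve (AUC) from 0.50 to 0.95. In one arm the cut-off was chosen on the validation sample. In the other it was locked from an independent sample of 100 and 100.

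- Tuned: the mean apparent Youden index exceeds the true one by 0.06 to 0.12 (0.37 against 0.27 at AUC 0.70; 0.51 against 0.43 at AUC 0.80).
- Locked: the mean difference is 0.00.
- Joint coverage of the two exact 95% intervals: 81% to 91% tuned, 93% to 94% locked. The loss is about 3 to 13 points and occurs at every AUC.

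No section proposes such tuning. Section G carries the selected markers forward from Phase 1, and section B(1) describes testing them against a blinded cohort.

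**The case for a change.** The strongest case for a change is that silence is risky in a study's only validation stage. The three blinding sentences do differ. No visible section names a recruiter, a code holder or the moment when disease status is released. The only allocation of statistical work covers two separate single-test analyses, by two companies that each supply one of the tests. No combination rule is stated, and a rule chosen after the data are seen could favour the combination. Writing these points down would need no extra subjects or procedures.

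Those observations stand as gaps in the text. What does not stand is the step from gap to failure. Section H(3) says who analyses each test. It does not say that these are the only analyses, and it does not bar linking them, while sections E and F both commit to the combined evaluation. Nor does an unnamed recruiter mean that a blinded investigator must recruit. The cut-off bias needs conduct that the plan does not describe and that its blinding is meant to prevent. The bounds on combined accuracy show only that a joint table is needed. They use assumed counts, and their ends require the most extreme dependence between the tests, so they do not measure an expected error. The IRB A-1 application may also settle the roles.

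**Conclusion.** The plan is short on operational detail here, but no stated rule produces a wrong result. A competent team following it would have unblinded staff confirm diagnosis and fill the 35/65 split, have the laboratories make their calls on coded samples, and then join both sets of calls to disease status to report breath, serum and combined accuracy. That order satisfies all three blinding sentences and delivers Aim 2. On that reading the cut-off bias is 0.00 and the combined result is one value, not a range.

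This rests on three assumptions: recruiters are distinct from those who run the assays and make the calls, the cut-offs are fixed before disease status is released, and the two laboratories' subject-level results can be linked. The text permits all three and requires none in so many words. Naming the roles and the combination rule would tidy the document, but it would mainly record what the plan already appears to intend. No change is required.
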